Primary Care Clinic	MH Providers	28
	PC Providers	28
MH Specialty Clinic	MH Providers	28
Total		157

Secondary data collection: The study population for all administrative data analyses will include a maximum of 4,200 patients and 900 providers. These numbers are estimates based on large facilities (e.g., the top 0.1% of patients at a large facility is approximately 150 patients and we are including 28 facilities) and therefore are likely overestimates. We plan to sample 10% of patients and their associated providers.

Inclusion/exclusion criteria. Inclusion criteria includes VA site staff, including REACH VET coordinators, Suicide Prevention Coordinators, mental health providers, and facility or VISN leadership who are: (a) at least 18 years of age, (b) have access to a telephone, (c) English speaking, and (d) mentally and physically able to complete the interview.

We will take special steps to insure that VA employees do not feel coerced to participate. VA employees generally need the permission of their supervisors to take time away from routine duties. Additionally, in order to meet with providers, appointments must be scheduled through designated clinic staff. Once staff members have been scheduled, they will be sent a letter with the elements of informed consent explaining that they have the right to decline participation. Potential subjects can contact study staff in advance to decline participation. At the time of each contact with study staff, they will be given the opportunity to decline participation in the study. The employee's supervisor will not be informed of the employee's decision and no negative employment consequences will result if an employee chooses not to participate.

This study will not enroll or involve any of the special classes of research subjects, such as pregnant women, prisoners, institutionalized individuals, or others who may be considered vulnerable populations per IRB regulations.

Participant Recruitment Methods

Sites will be recruited via REACH VET Coordinator monthly calls and email communications. Within each site, staff participants will be recruited by identifying the local REACH VET Coordinator, Suicide Prevention Coordinator, providers identified in the REACH VET dashboard, and by contacting local or regional mental health leadership.

Compensation. No compensation will be offered to participants for participating in this evaluation.

Withdrawal of Subjects

Participants may withdraw from the evaluation at any time by verbal or written request, which will be documented in the case file by the investigator. Withdrawal will not be communicated to any site staff in order to maintain confidentiality and avoid the potential for coercion.

Privacy and Confidentiality (Data Management and Monitoring)

Investigators will not disclose participants' PII. All investigators and staff will have complied with all VA research training requirements prior to beginning participation in this evaluation.

All information on individual subjects will be kept confidential on restricted-access server files behind the VA firewall. Study staff will obtain a list of the names and addresses of REACH VET staff from mental health leadership at each site in order to recruit providers to complete telephone interviews. The study PI and Qualitative Lead will maintain an electronic file linking identification numbers to the names of the provider interview participants (participant "crosswalk"). These files will be in a folder that is separate from other evaluation data. Access to the analytic files within VA will be limited to the principal investigator and those team members involved in the analyses. Individually unique user identification codes and passwords are necessary to access the network. Accounts and passwords comply with existing VA policy and procedures.

Hard copies of participant responses will be kept in a locked area of CeMHOR space at CAVHS. Hard copies will be maintained in accordance with the VA Record retention schedule (www1.va.gov/VHAPUBLICATIONS/RCS10/rcs10-1.pdf). Only project staff with credentials and permission to use the data will have access to the data.

Data Security and Sharing

How Data Will Be Stored. Contact and consent information will be stored in a restricted-access folder on the password-protected HSR&D server at the Central Arkansas Veterans Healthcare System (CAVHS), North Little Rock, AR campus (\\R02LITHSMDC101.V16.MED.VA.GOV\SERVICES\HSR). The information will remain stored and maintained per VA policies and procedures. Participants will be given a non-identifying code linking them to the audio recording of the interviews. The paper data will be kept in the study PI's Office in [name]. Qualitative interviews will be stored temporarily on VA approved digital audio recorders (Phillips DPM 8000). These temporary electronic files will be purged from the recorder upon upload to a password protected file on the secure network server on the CAVHS campus. Audio data will not include identifying information. Instead each participant will be given a corresponding number.

Who Will Have Access. [name] and [name] will have access to the REACH VET dashboard and CPRS records for screening, medical chart reviews and to conduct periodic reviews for AEs and SAEs. [name] will have access to the REACH VET dashboard and CPRS records for the Caring Letters component of this evaluation. [name] will have access to the REACH VET dashboard to analyze data related to the dashboard. [name], [name], [name], [name], and [name] will have access to time tracking logs for cost evaluations. [name], [name], [name], [name], and [name] will have access to contact information of the site staff, REACH VET coordinators, and facilitators for interviewing purposes. [name], [name], [name], [name], and [name] will have access to the list that correlates the identifying number to the participant. This crosswalk file will be maintained in a separate password protected file on the secure network server on the CAVHS campus. All records will be accessible for inspections and copying by authorized representatives of VA, OHRP, and other authorized entities. If any member of the evaluation team leaves the study, his/her access to study data will be removed immediately. If, in spite of the implemented precautions, participant data is lost, stolen, or compromised, it will be reported immediately to the PI. The PI or designee will report the event to the IRB, the ISO, the PO, and the ACOS/R&D immediately upon discovery, but no longer than 1 hour after learning of the breach of confidentiality.

How Long It Will Be Stored. VA Records Control Schedule DAA-0015-2015-0004, disposition authority number-0032 requires that records be maintained for 6 years following the end of the fiscal year after completion of the project. Audio recordings of interviews and other electronic records will be

retained on a VA server for this period of time. All hard copies of records will be stored in locked filing cabinets on VA property until the close of the study, at which time they will be surrendered to Research Administration for storage for six years following the end of the fiscal year after completion of the project.

Communication Plan

All site approvals (CAVHS and VAPAHCS) will be obtained in compliance with local IRB and R&D procedures. For each site participating but not engaged in research (in this study, the 28 sites receiving virtual implementation facilitation), we will notify the Director prior to conducting evaluation activities at his/her facility (see Director's Letter). Also, we will process any changes in the protocol, consent processes, or cessation of engagement in research for any sites in concordance with local IRB and site procedures.

The PI will meet regularly with the evaluation team, which includes the Local Site Investigator from Palo Alto ([name]), and through this mechanism we will facilitate all above communications.

References

1. McCarthy, J. F. *et al.* Predictive Modeling and Concentration of the Risk of Suicide: Implications for Preventive Interventions in the US Department of Veterans Affairs. *American journal of public health* e1–e8 (2015).
3. Carter, G. L., Clover, K., Whyte, I. M., Dawson, A. H. & D'Este, C. Postcards from the EDge project: randomised controlled trial of an intervention using postcards to reduce repetition of hospital treated deliberate self poisoning. *BMJ* **331**, 805 (2005).
4. Carter, G. L., Clover, K., Whyte, I. M., Dawson, A. H. & D'Este, C. Postcards from the EDge: 24-month outcomes of a randomised controlled trial for hospital-treated self-poisoning. *Br J Psychiatry* **191**, 548–553 (2007).

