The plan for national roll out of REACH VET was developed by OSP, with input from the evaluation team and other partners. National implementation of REACH VET began in November 2016 and included identification of a REACH VET coordinator at each facility, REACH VET dashboard training for coordinators and interested providers, and rollout of the dashboard. Each facility initially received the top eight names of patients identified as being in the top 0.1% of risk for suicide at that facility. Over the following three months, facilities will receive additional names via the dashboard until all patients in the top 0.1% have been identified; facilities can opt to receive the full list at any time. Standard implementation strategies will include training and education, chart note templates to support documentation, an intranet site of resources for coordinators and providers, technical assistance as requested, and clinical consultation as requested. Barriers and facilitators will be assessed during this time by the evaluation team.

Figure 2. Trial design.

		Study Month							
Network	Sites	1-3	3 – 6	6 - 9	9 - 12	12 - 15	15 - 18	18 - 21	21 - 24
A	1-4	Facilitation							
B	5-8	Awaiting Facilitation		Facilitation					
C	9-12	Awaiting Facilitation		Facilitation					
D	13-16	Awaiting Facilitation			Facilitation				
E	17-20	Awaiting Facilitation				Facilitation			
F	21-24	Awaiting Facilitation					Facilitation		
G	25-28	Awaiting Facilitation						Facilitation	

Virtual

External Facilitation Implementation Strategy

Additional implementation support will begin in April 2017. We will target 7 networks and 4 sites in each network not meeting the criterion for timely notification. The participating VISNs will be randomized to when the sites in their network will receive facilitation.

The facilitators will be two master’s level and one doctoral level clinicians with clinical expertise in suicide prevention and REACH VET; the facilitators are funded through OSP and are not part of the evaluation team. They attended facilitation training February 1-2, 2017. The training included how to conduct virtual facilitation and utilized a virtual external facilitation manual developed by a workgroup of the Behavioral Health QUERI’s Implementation Facilitation Learning Collaborative.

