Measures: Data sources will include qualitative interviews with site staff, including REACH VET coordinators, SPCs, mental health and primary care providers, and facility or VISN leadership. We will aim to conduct at least three interviews per facility, with a maximum of five interviews per facility. Interviews will be conducted by phone and be audio-recorded and transcribed. Interviews will be conducted to refine the virtual external facilitation strategies to be used. During virtual external facilitation, we will conduct monthly debriefings with the facilitators.

Analysis: Rapid Qualitative Analysis (RQA)³⁹ strategies will be used to ensure timely communication of findings to our OSP partners and to allow us to refine our virtual external facilitation strategies as needed. Each interview transcription will be read by two members of the qualitative team, who will then distill information pertaining to previously identified domains of interest based on iPARIHS (context, innovation, recipient), as well as emergent themes, into an episode profile. Episode profiles will be compared and any discrepancies resolved by referring back to the original transcript and/or presenting the profile to the larger team for discussion. Completed episode profiles will be entered into tables to create a composite matrix of data for each site, in order to be able to compare across participant responses. We will then share these episode profiles and site matrices with the qualitative coding team, REACH VET Program Manager, and external facilitators via a Lync meeting to discuss potential refinements to facilitation strategies.

Specific Aim 1b: Conduct a summative evaluation of virtual external facilitation versus standard implementation.

Design: All VA sites (N = 144) within VA's 18 regional networks that were directed to implement REACH VET will receive standard implementation. Network directors will be asked if they would like to receive additional implementation help for sites in their VISN having difficulty implementing REACH VET (e.g., not meeting the criterion of completing at least 80% of provider notifications of patient high-risk status within 7 days during the last month). VISNs participating will be randomized to when the VISN receives virtual external facilitation at 4 of their sites having difficulty implementing.

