STATISTICAL ANALYSIS PLAN

Risk Stratified Enhancements to Clinical Care: Targeting Care for Patients Identified Through Predictive Modeling as Being at High Risk for Suicide, with the Office of Mental Health Operations

SDR 16-195

NCT03280225

[name]
Principal Investigator

Funding Agency: HSR&D

Version 2.0

07/16/2021

Preface

The VHA predictive model identifies the top 5% of VHA patients at the highest predicted risk for suicide. These Veterans identified by VHA accounted for approximately 24% of all the suicide deaths, 37% of all reported suicide attempts, and 31% of inpatient psychiatric hospitalizations observed in VHA over the course of one year. Veterans in the highest 0.01% of the risk stratum had suicide rates 82 times greater than the rest of the sample in a development model.

Using this predictive model, VHA's Office of Mental Health and Suicide Prevention implemented a national suicide prevention outreach program entitled Recovery Engagement and Coordination for Health – Veterans Enhanced Treatment (REACH VET). REACH VET utilizes a dashboard to provide the names of patients identified by the model monthly to coordinators at each VA medical facility. REACH VET coordinators are responsible for notifying providers of the patient's status and prompting providers to re-evaluate care and take appropriate clinical steps if they are not already occurring (e.g., contacting the patient to re-engage in care, discussing potential changes in care with the patient).

Implementation assistance in the form of virtual external facilitation, an evidence-based implementation strategy, was offered to sites having difficulty implementing REACH VET during the system-wide rollout of the program. The analysis plan for specific aim 1b is below.

Scope and Analysis

Low performing VHA facilities were identified by leadership in seven Veteran Integrated Service Networks (VISN). Implementation assistance in the form of virtual external facilitation, an evidence-based implementation strategy, was offered to sites having using a stepped wedge design clustering sites at the VISN level. Two VISNs no longer needed facilitation by the time they reached the opportunity to receive it; these VISNs and facilities were excluded from any analyses. REACH VET Historic Summary Reports contain summary metrics used to evaluate facility performance on the four measures listed below.

REACH VET Outcome Measures

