Note, we do not model a transition period from pre-to-post Average number of implementation days = 175 (SD 49.3). Index date is based upon date of site visit.

Analysis

Our quasi-experimental pre-post intervention analysis evaluated four outcome measures as tracked by the REACH VET program across 23 VAMCs, during 6-month periods prior to implementation and again after the onset of implementation. We used the REACH VET Historic Summary Report to collect metrics for Coordinator assignment, Provider assignment, Care evaluation, and Attempted outreach all within one week of each monthly report's release date. To compare statistical differences in outcomes between pre-and post-periods we used generalized estimating equations (GEE) to control for clustering of observations within VAMCs. Fixed effects included a time-dependent variable identifying change in intervention status (pre-post) as well an independent variable of time to account for the possibility of improvement due to secular trends.

References

Cui, J. (2007). QIC Program and Model Selection in GEE Analyses. *The Stata Journal*:

Promoting Communications on Statistics and Stata, 7(2), 209–220.
<https://doi.org/10.1177/1536867X0700700205>

Pan, W. (2001). Akaike's information criterion in generalized estimating equations.
Biometrics, 57(1), 120–125. <https://doi.org/10.1111/j.0006-341x.2001.00120.x>

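### Sites picked for recent poor performance enter an uncontrolled pre-post model with no guard against regression to the mean, and that model can magnify the rebound if the selection month falls late in the pre-window

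*Protocol*

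**What the plan says.** **Selection.** The Design paragraph of Specific Aim 1b in the protocol offers help to sites having difficulty and gives as its example those "not meeting the criterion of completing at least 80% of provider notifications of patient high-risk status within 7 days during the last month". The protocol's section on the facilitation strategy treats this as the rule: "We will target 7 networks and 4 sites in each network not meeting the criterion for timely notification". The SAP (Scope and Analysis) describes a looser process, with no month or threshold: "Low performing VHA facilities were identified by leadership in seven Veteran Integrated Service Networks".

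**Timing.** The order of starts is random by network: "The participating VISNs will be randomized to when the sites in their network will receive facilitation". The protocol puts national roll-out in November 2016, with each facility's list growing over the next three months, and adds: "Additional implementation support will begin in April 2017". The SAP reports that "Two VISNs no longer needed facilitation by the time they reached the opportunity to receive it" and excludes those networks from every analysis.

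**Analysis.** The SAP sets aside the stepped-wedge analysis because network-level clustering gave too small a sample. It compares 23 sites "during 6-month periods prior to implementation and again after the onset of implementation", using GEE with compound symmetry within site, a time variable in months and a 0/1 phase indicator. There is no transition period, and "Index date is based upon date of site visit".

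Neither document dates the selection month relative to a site's index date, mentions regression to the mean, removes the selection month from the pre-window, or adds comparison sites that were never facilitated.

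**The concern.** A site picked because it has just done badly will, on average, do better next month with no help at all. If the poor month sits in the pre-window, that recovery appears as improvement after facilitation, and an uncontrolled comparison cannot tell the two apart. The exclusion of two networks adds to this: need was evidently looked at again as turns came up, so the analysed sites are partly those that had not recovered by themselves.

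The month term does not protect against this. A low value just before the index date pulls the fitted line down at the join and widens the step. The bias can then exceed that of a simple difference of means. At stake is the Aim 1b conclusion that facilitation improved implementation.

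**Working it through.** The plan gives no effect size, variance, correlation or power figure, so there is none of its own to reproduce. The check asks how far a dip in one pre-month moves the step.

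**Inputs from the documents:** 23 sites in clusters of 5, 4, 4, 6 and 4; six pre and six post months; linear month plus step; compound symmetry.

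**Assumed:** identity link; complete windows; index months 7, 10, 13, 16 and 19 for calendar time; within-site correlation 0.3, varied from 0 to 0.6. The SAP does not say whether month is calendar time or counted from the index, so both are shown.

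**Months from index.** Let p = -0.5 (pre) or +0.5 (post), and let t run from -5.5 to +5.5.
- Sum of t² = 143, sum of pt = 18, sum of p² = 3.
- Step weight of a month = (p - (18/143)t) / (3 - 18²/143) = (p - 0.1259t) / 0.7343.
- Last pre-month (t = -0.5): (-0.5 + 0.0629) / 0.7343 = -0.595.
- First pre-month (t = -5.5): (-0.5 + 0.6923) / 0.7343 = +0.262.
- Without the month term, every pre-month has weight -1/6 = -0.167.

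Every site has the same design here, so the assumed correlation does not alter these weights.

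**Calendar month.** b = (Σ X'V⁻¹X)⁻¹ Σ X'V⁻¹y, with V = (1 - ρ)I + ρJ. Staggered starts let differences between sites inform the slope, so the result depends on ρ.

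Bias in the step (points) from a 10-point dip at all 23 sites:

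| Pre-month with the dip | Months from index | Calendar month, ρ = 0.3 | Mean difference |
|---|---|---|---|
| 1 (earliest) | -2.6 | -0.5 | 1.7 |
| 2 | -0.9 | 0.4 | 1.7 |
| 3 | 0.8 | 1.2 | 1.7 |
| 4 | 2.5 | 2.1 | 1.7 |
| 5 | 4.2 | 2.9 | 1.7 |
| 6 (last) | 5.95 | 3.80 | 1.7 |

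- Calendar month, last pre-month: 2.3 at ρ = 0 to 4.9 at ρ = 0.6.
- First cluster only, last pre-month: 5.95 × 5/23 = 1.29 (months from index), or 0.2 to 1.0 (calendar month, ρ = 0 to 0.6).

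**How large might a dip be?** This rests entirely on assumptions. Single sites were selected on below 80% in the last pre-month, with typical site level 65 to 85%, site SD 0.6 logit, monthly SD 0.3 to 0.6 logit and 8 to 150 Veterans per month. The expected dip was 0.8 to 14.0 points. At weight 0.595 that is a false step of 0.5 to 8.3 points.

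**Null simulation.** Middle case (75%, monthly SD 0.6, 30 Veterans), 400 runs per setting, no true effect, assumed starts at months 1, 4, 7, 10 and 13:

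| Selection | Bias in step (points) | Rejection at nominal 5% |
|---|---|---|
| None | 0.1 to 0.2 | 6 to 7% |
| Once, before the first wave | 0.8 to 1.0 | 8% |
| Each site just before its start | 2.3 (calendar) to 4.2 (from index) | 18 to 26% |

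**The case against.** A reader might infer that every analysed site had its bad month inside the pre-window, and so that any estimated effect is regression to the mean. The documents do not support that.

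- **The month is undated.** The one-month rule is an example in the Aim 1b Design paragraph, and the SAP says leadership chose the sites. With one selection followed by a randomised wait, the month falls outside the six-month pre-window for most waves, and the bias is about 1 point.
- **The second look is thinly documented.** The SAP says two networks no longer needed help. It does not say that sites in the other five were re-tested, singly or in the month before the site visit. A simulation that dropped only the two best of seven networks, with independent sites, gave a dip of 0.7 to 3.3 points. At weight 0.38 that is 0.3 to 1.3 points, and at 0.595 it is 0.4 to 2.0. Shocks shared within a network would raise this, but nothing in the documents sizes them.
- **Magnification is not general.** It is confined to the last three pre-months, and an early dip adds less or pushes the step down.
- **The selection metric is not an outcome.** It is provider notification within 7 days. The outcomes are assignment, care evaluation and outreach, which the SAP takes from a days 1-14 view in one section and within one week in another. Carry-over to each is unknown.

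All four points stand, and they limit the size that can be claimed. They do not remove the gap. For the first wave, overlap is hard to avoid if it started on schedule: only about five months separate roll-out from April 2017, so almost any earlier report lies in its pre-window. For later waves, only the sponsor can supply the dates.

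**Conclusion.** The concern holds in conditional form. Sites entered for recent poor performance, networks that no longer needed help were dropped, and the chosen model has no safeguard against regression to the mean. If selection or confirmation months are among the last pre-months, the bias is upward and larger than a mean difference would show: per 10-point dip in the last pre-month at all sites, about 3.8 points (calendar month; 2.3 to 4.9 across correlations 0 to 0.6) or 6.0 (months from index), against 1.7. If only the first wave is affected, it is about 0.2 to 1.3 points.

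These figures assume a linear model, complete windows, three-monthly starts and full carry-over of the dip to the outcome. The dip itself cannot be sized from the documents. The result is a possible bias of unknown size, which the sponsor can check from its own records. It does not show that the facilitation effect is spurious.

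**What to change.** State, for each of the 23 sites, the month whose performance was used to select it and any month used to confirm that its network still needed facilitation, both relative to the index date. Say whether the time variable is calendar month or month from index.

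Where such a month lies in the six-month pre-window, re-fit the model for all four outcomes without it. Extend the pre-window back only where comparable reports exist after the roll-out ramp-up, which is unlikely for the first wave. Report this beside the current window, and do not attribute the step to facilitation if it does not survive.

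**Cost.** SAP wording and a re-run on reports already held. Dropping the last pre-month without replacement raises the step's standard error by about 8 to 15% (calendar month, ρ = 0 to 0.6) or 18% (months from index). Some bias remains if poor performance carries over between months, because neighbouring months are then low too.
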